7.2.1.1. Treatment-Emergent Laboratory Abnormalities

Treatment-emergent laboratory abnormalities are defined as values that increase at least 1 toxicity grade from Baseline at any postbaseline time point, up to and including the date of last dose of ABI-H2158/PBO plus 28 days or subjects who permanently discontinued ABI-H2158/PBO. If the relevant baseline laboratory value is missing, any abnormality of at least Grade 1 observed within the time frame specified above will be considered treatment emergent.

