3.1.2 Secondary Objectives

- To evaluate the PK of ABI-H2158 and ETV in subjects with CHB
- To evaluate the effect of ABI-H2158 in reducing HBV pgRNA levels in subjects with CHB
- To evaluate the effect of ABI-H2158 in reducing HBV antigens (ie, HBeAg, HBcrAg, and HBsAg) in subjects with CHB
- To evaluate the effect of ABI-H2158 on normalization of ALT in subjects with abnormal ALT
- To evaluate the emergence of resistance to ABI-H2158 when administered in combination with ETV

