9.4 Management of ALT Elevations

All subjects participating in the study will be closely monitored for ALT elevations and/or signs of potential decline in hepatic function (see [Figure 2](#)). Subjects experiencing ALT elevations $\geq 2 \times$ Baseline (Day 1) or on-treatment nadir and $> 2 \times$ ULN during study treatment or during post-treatment follow-up should be closely monitored with regular Unscheduled Visits every 1-2 weeks at the discretion of the Investigator. At these visits, the following laboratory tests will be performed: ALT, AST, total bilirubin (if total bilirubin is elevated, reflex to direct bilirubin), serum albumin, INR and creatine kinase. The Investigator will determine if other Unscheduled Visit assessments should be performed. Additionally, the following guidance is provided for management of subjects with ALT elevations:

- ALT Elevation without Declining Hepatic Function
 - All subjects with an ALT elevation on treatment, defined as ALT $> 2 \times$ Baseline or on-treatment nadir and $\geq 10 \times$ ULN, should have the ALT findings confirmed within 3 days of receipt of the original results. All subjects should return for an Unscheduled Visit ([Section 7.6](#)).
 - If the ALT elevation is confirmed, then an additional Unscheduled Visit will be performed to further evaluate the subject. At this visit, the following laboratory tests will be performed: ALT, AST, total bilirubin (if total bilirubin is elevated, reflex to direct bilirubin), serum

albumin, INR, creatine kinase, HBV DNA, quantitative HBV serologies (HBeAg [reflex qualitative HBeAg if quantitative HBeAg is negative] and HBsAg [reflex qualitative HBsAg if quantitative HBsAg is negative]), HAV IgM, HCV RNA, HDV RNA, and HEV IgM. The Investigator will determine if other Unscheduled Visit assessments should be performed.

- If an intercurrent cause is determined to be causal, subjects with an ALT elevation without declining hepatic function and without contraindications may continue treatment and the intercurrent illness should be treated as deemed medically appropriate by the Investigator.
- Subjects with an ALT elevation without declining hepatic function and without contraindications may continue treatment with study drug under close observation.

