Injection Site Induration or Swelling Report only one	Same as for Injection Site Erythema or Redness , >15 years of age	Same as for Injection Site Erythema or Redness , >15 years of age	Same as for Injection Site Erythema or Redness , >15 years of age	Same as for Injection Site Erythema or Redness , >15 years of age
Injection Site Pruritus	Itching localized to the injection site that is relieved spontaneously or in <48 hours of treatment	Itching beyond the injection site that is not generalized OR Itching localized to the injection site requiring ≥48 hours treatment	Generalized itching causing inability to perform usual social & functional activities	NA

¹² Injection Site Erythema or Redness should be evaluated and graded using the greatest single diameter or measured surface area.

Laboratory Values*: Chemistries				
Parameter	Grade 1 Mild	Grade 2 Moderate	Grade 3 Severe	Grade 4 Potentially Life-Threatening
Acidosis	NA	pH≤7.3 to <LLN	pH<7.3 without life- threatening consequences	pH<7.3 with life- threatening consequences
Albumin, Low (g/dL; g/L)	3.0 to <LLN 30 to <LLN	≥ 2.0 to <3.0 ≥ 20 to <30	< 2.0 < 20	NA
Alkaline Phosphatase, High	1.25 to < 2.5 x ULN	2.5 to < 5.0 x ULN	5.0 to < 10.0 x ULN	≥ 10.0 x ULN
Alkalosis	NA	pH > ULN to □ 7.5	pH > 7.5 without life- threatening consequences	pH > 7.5 with life- threatening consequences
ALT or SGPT, High Report only one	1.25 to < 2.5 x ULN	2.5 to < 5.0 x ULN	5.0 to < 10.0 x ULN	≥ 10.0 x ULN
Amylase (Pancreatic) or Amylase (Total), High Report only one	1.1 to <1.5×ULN	1.5 to <3.0×ULN	3.0 to <5.0×ULN	≥5.0×ULN
AST or SGOT, High Report only one	1.25 to < 2.5 x ULN	2.5 to < 5.0 x ULN	5.0 to < 10.0 x ULN	≥ 10.0 x ULN
Bicarbonate, Low (mEq/L; mmol/L)	16.0 to <LLN 16.0 to <LLN	11.0 to <16.0 11.0 to <16.0	8.0 to <11.0 8.0 to <11.0	<8.0 <8.0
Bilirubin Direct Bilirubin, High	NA	NA	> ULN with other signs and symptoms of hepatotoxicity.	> ULN with life- threatening consequences (eg, signs and symptoms of liver failure)
Total Bilirubin, High	1.1 to <1.6×ULN	1.6 to <2.6×ULN	2.6 to <5.0×ULN	≥5.0×ULN
Calcium, High (mg/dL; mmol/L)	10.6 to <11.5 2.65 to <2.88	11.5 to <12.5 2.88 to <3.13	12.5 to <13.5 3.13 to <3.38	≥3.5 ≥3.38
Calcium (Ionized), High (mg/dL; mmol/L)	>ULN to <6.0 >ULN to <1.5	6.0 to <6.4 1.5 to <1.6	6.4 to <7.2 1.6 to <1.8	≥7.2 ≥1.8
Calcium, Low (mg/dL; mmol/L)	7.8 to <8.4 1.95 to <2.10	7.0 to <7.8 1.75 to <1.95	6.1 to <7.0 1.53 to <1.75	<6.1 <1.53

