3.6.2. Analysis Visit Windows

Subject visits might not occur on protocol-specified days. Therefore, for the purpose of analysis, observations will be assigned to analysis windows. In general, the baseline value will be the last nonmissing value on or prior to the first dose date of study drug. The “on-treatment” period is defined up to the last dose date of ABI-H2158/PBO. The “off-treatment” period is defined after the last dose of ABI-H2158/PBO through the follow up period.

The assessment schedule is different in the Korea country specific protocol amendment. The analysis window will follow what is specified in the global protocol.

The analysis windows for on-treatment study assessments, including HBV DNA, HBV pgRNA, HBsAg, HBeAg, HBcrAg, adverse events, and clinical laboratories (chemistry, hematology, coagulation, urinalysis) are provided in [Table 3-1](#).

Table 3-1. On-Treatment Analysis Visit Windows for Study Assessments

Nominal Visit	On-Treatment Nominal Study Day	Visit Window Study Day	
		Lower Limit	Upper Limit
Day 1	1	(none)	1
Week 2	14	2	21
Week 4	28	22	42
Week 8	56	43	70
Week 12	84	71	98
Week 16	112	99	126
Week 20	140	127	154
Week 24	168	155	182
Week 28	196	183	210
Week 32	224	211	238
Week 36	252	239	266
Week 40	280	267	294
Week 44	308	295	322
Week 48	336	323	350
Week 52	364	351	378
Week 56	392	379	406
Week 60	420	407	434
Week 64	448	435	462
Week 68	476	463	490

Nominal Visit	On-Treatment Nominal Study Day	Visit Window Study Day	
		Lower Limit	Upper Limit
Week 72	504	491	≥504

The analysis windows for electrocardiograms (ECG) measurements are provided in [Table 3-2](#).

Table 3-2. On-Treatment Analysis Visit Windows for ECG

Nominal Visit	On-Treatment Nominal Study Day	Visit Window Study Day	
		Lower Limit	Upper Limit
Day 1	1	(none)	1
Week 12	84	2	126
Week 24	168	127	210
Week 36	252	211	294
Week 48	336	295	378
Week 60	420	379	462
Week 72	504	463	≥504

The analysis windows for off-treatment study assessments, including HBV DNA, HBV pgRNA, HBsAg, HBeAg, HBcrAg, vital signs, concomitant medications and adverse events, chemistry, hematology, coagulation and urinalysis are provided in [Table 3-3](#).

Table 3-3. Off-Treatment Analysis Visit Windows for Study Assessments

Nominal Visit	Off-Treatment Nominal Study Day	Visit Window Study Day	
		Lower Limit	Upper Limit
FU-Week 4	28	1	42
FU-Week 8	56	43	70
FU-Week 12	84	71	≥84

The analysis windows for ECG is provided in [Table 3-4](#).

Table 3-4. Off-Treatment Analysis Visit Windows for ECG

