7.2.2.2. ALT Elevation with Declining Hepatic Function

A confirmed ALT elevation with evidence of declining hepatic function is defined as meeting the following criteria at 2 consecutive visits:

- ALT elevation $\geq 2 \times \text{Baseline (Day 1)}$ or nadir and $> 2 \times \text{ULN(Covance)}$ AND
- Direct bilirubin increase to $\geq 2 \times \text{Baseline (Day 1)}$ and $\geq 2 \times \text{ULN(Covance)}$ OR
- Albumin decline $\geq 0.5 \text{ g/dL}$ OR $\text{INR} > 2 \times \text{Baseline (Day 1)}$ OR
- Symptoms of liver inflammation (eg, fatigue, weakness, lack of appetite, nausea, vomiting, jaundice or discolored feces)

The number and subjects meeting the above laboratory criteria will be summarized by treatment group. Clinical signs or symptoms of liver inflammation will not be included in the summary. For individual laboratory tests, subjects will be counted once based on the most severe postbaseline values. For the composite criteria, subjects will be counted once when the criteria are met at the same visit. The denominator is the number of subjects in the Safety Analysis Set who have nonmissing postbaseline values. A listing of subjects who met at least 1 of the above criteria will be provided.

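### The treatment-emergent laboratory table measures ALT against Baseline only, so it omits on-drug rebounds from a normalised nadir that do not exceed the Baseline grade; SAP 7.2.2.2 covers only part of that gap.

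*Combined protocol and SAP*

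**What the plan says.** SAP section 7.2.1.1 gives the rule: "Treatment-emergent laboratory abnormalities are defined as values that increase at least 1 toxicity grade from Baseline at any postbaseline time point". The window runs "up to and including the date of last dose of ABI-H2158/PBO plus 28 days". SAP section 3.6.2 fixes the reference point: "the baseline value will be the last nonmissing value on or prior to the first dose date of study drug". For these treatment-naïve subjects that is ALT before entecavir.

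Protocol Appendix 2 grades ALT as Grade 1 at "1.25 to < 2.5 x ULN", Grade 2 at "2.5 to < 5.0 x ULN", Grade 3 from 5 to below 10× ULN, and Grade 4 from 10× ULN. Exclusion criterion 13e removes only Screening ALT above 5× ULN. Protocol section 3.1.2 lists as an objective: "To evaluate the effect of ABI-H2158 on normalization of ALT in subjects with abnormal ALT".

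Elsewhere the plan does use a nadir. The first monitoring tier in protocol section 9.4 applies when ALT is at least twice "Baseline (Day 1) or on-treatment nadir and" above 2× ULN. SAP section 7.2.2.1 accepts Baseline or on-treatment nadir but needs at least 10× ULN. SAP section 7.2.2.2 uses the 9.4 thresholds as the ALT part of its declining-function criterion, at two consecutive visits, and summarises the laboratory criteria by treatment group. Its counting rule reads: "For individual laboratory tests, subjects will be counted once based on the most severe postbaseline values".

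**The concern.** ALT is expected to fall on treatment in subjects who enter with active hepatitis. If it falls to normal and then rises while the subject is on ABI-H2158, the relevant change is from the nadir. A Baseline-only rule compares the rise with the pre-treatment peak. The same on-drug value is then treatment-emergent in a subject who entered with normal ALT and not in one who entered at Grade 2.

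Safety is a primary objective, and SAP section 1 records that development stopped after ALT elevations consistent with drug-induced liver injury. The by-arm ALT tables are therefore the ones a reader will examine most closely, and each planned placebo group has only 10 subjects per cohort.

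**Working it through.** The documents state no figure on this point, so there is none to reproduce. The check applies the plan's own rules to illustrative ALT paths. All values are multiples of ULN, and a nadir of 0.8 is assumed.

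**Rules.** Treatment-emergent (7.2.1.1): grade(rebound) − grade(Baseline) ≥ 1. ALT part of 7.2.2.2: rebound ≥ 2 × Baseline or ≥ 2 × nadir, and rebound > 2.

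| Baseline | Rebound | Rebound ÷ nadir | Grade change from Baseline | Treatment-emergent | ALT part of 7.2.2.2 |
|---|---|---|---|---|---|
| 1.1 (G0) | 1.5 (G1) | 1.9 | +1 | yes | no |
| 1.5 (G1) | 2.2 (G1) | 2.8 | 0 | **no** | yes |
| 1.5 (G1) | 3.0 (G2) | 3.8 | +1 | yes | yes |
| 3.0 (G2) | 1.5 (G1) | 1.9 | −1 | **no** | no |
| 3.0 (G2) | 4.5 (G2) | 5.6 | 0 | **no** | yes |
| 3.0 (G2) | 5.5 (G3) | 6.9 | +1 | yes | yes |

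**Omitted band.** From a Grade 0 nadir, the table leaves out rebounds of 1.25 to <2.5 for a Grade 1 entrant and 1.25 to <5 for a Grade 2 entrant. A Grade 3 Baseline is an edge case (exactly 5.0 at Screening, or a rise between Screening and Day 1). There the band runs to <10.

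**What the other outputs recover.**

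- *7.2.2.1.* It needs at least 10× ULN, which is Grade 4. That already exceeds any Baseline of Grade 3 or lower, so it recovers none of the omitted cases.
- *Maximum postbaseline grade (7.2.1.2).* Take Baseline 3.0, Week 2 2.8, nadir 0.8, rebound 4.5. The maximum is Grade 2 with or without the rebound, so the table cannot tell the two apart.
- *7.2.2.2.* For any nadir at or below ULN, 2 × nadir ≤ 2, so the >2× ULN floor decides. Its ALT part can reach rebounds above 2 but not those from 1.25 to 2, and it asks for two consecutive visits.

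**The value chosen in 7.2.2.2.** Take Baseline 4.0, Week 2 3.8, nadir 0.8, rebound 3.5. The most severe postbaseline value is 3.8, which precedes the nadir.

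- Against the nadir to date: 3.8 ÷ 4.0 = 0.95, not met. The later rebound, 3.5 ÷ 0.8 = 4.4, would qualify but is not the value selected.
- Against the overall nadir: 3.8 ÷ 0.8 = 4.8, met. The same result follows with no rebound at all, so a subject whose ALT simply normalised is counted as an elevation (given a second consecutive qualifying value, if the two-visit rule applies to this row).

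The SAP does not say which nadir applies.

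**The case against.** A reader might infer that these rebounds go uncounted anywhere in the SAP. The documents do not support that. SAP section 7.2.2.2 provides a by-arm, nadir-based ALT count, with individual tests as well as the composite. A Baseline of 4.0, nadir 0.8 and rebound 4.9 (6.1 × nadir) is omitted under 7.2.1.1 but would probably be counted there if sustained. Only an early value between 4.9 and 5.0 could displace it as the most severe without itself being Grade 3 and so treatment-emergent. Protocol section 9.4 also calls for extra visits every 1–2 weeks at the Investigator's discretion, so a second value will often exist.

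The adverse event tables are a further by-arm route. SAP section 7.1.5.1 defines treatment emergence of AEs by onset date, and 7.1.6 tabulates them by preferred term, arm and severity. Grade worsening from Baseline is also the definition the sponsor used in its Phase 1b study (protocol Table 4 footnote). It applies equally to both arms, and the SAP is deliberately reduced to support a synoptic report.

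Most of this stands, and it is the reason to keep the Baseline-grade table. It does not close the gap. The AE route depends on the Investigator judging a value clinically significant (protocol section 8.5). The listings give no count by arm. The visit-by-visit ALT normalisation endpoint, which might have shown loss of normalisation, is dropped in SAP section 6.2. Applying the rule equally to both arms does not restore the rebounds it misses. The 7.2.2.2 wording can be read more favourably, but the SAP does not settle the reading.

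**Conclusion.** The point holds in bounded form. The treatment-emergent table omits on-drug ALT rebounds at or below the Baseline grade: below 2.5× ULN for Grade 1 entrants and below 5× ULN for Grade 2 entrants. For Grade 1 or 2 entrants every rebound of 5× ULN or more is counted. Entrants with ALT below 1.25× ULN, including those slightly above ULN, are unaffected. SAP section 7.2.2.2 covers the part above 2× ULN, subject to two consecutive visits and to an unclear choice of value and nadir.

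The bands follow from the Appendix 2 cut-points and assume a nadir in the Grade 0 range. The number of affected subjects cannot be given, because the documents report neither the share entering with raised ALT nor any ALT values from this study. An assumed share of the planned enrolment would count subjects under the rule, not rebounds missed.

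A reader might also infer that the table understates the liver signal that ended development. That is not shown, since the ALT values behind that decision are not given.

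**What to change.** Keep the Baseline-grade table. In SAP section 7.2.1.2 add one table, by cohort, arm and Baseline ALT grade. It should give the number of subjects with ALT at least 2× the running nadir (the lowest of Baseline and all earlier postbaseline values) and above 2× ULN, at any visit through last ABI-H2158/PBO dose plus 28 days. Show single-visit and confirmed events separately. A rise of at least one grade from the running nadir may be a supporting row only, because a move from 0.8 to 1.3× ULN would qualify.

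In the individual ALT row of section 7.2.2.2, judge each visit against the nadir to date in place of the single most severe value.

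The cost is one derived variable and one table from data already collected. Ordinary HBV fluctuation will add some events in both arms, and the PBO+ETV arm shows that background. If the SAP is already final, section 1 provides for recording the change in the Synoptic CSR. No clinical management rule is altered.

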7.2.1.2. Summaries of Laboratory Abnormalities

A summary (number and percentage of subjects) for treatment-emergent graded laboratory abnormalities will be provided by lab test and treatment group; subjects will be categorized according to the most severe postbaseline abnormality grade for a given laboratory test:

For all summaries of laboratory abnormalities, the denominator is the number of subjects with nonmissing postbaseline values up to 28 days after last dose date of ABI-H2158/PBO.

The maximum postbaseline grade observed up to 28 days after last dose date will be tabulated for each laboratory test, and percentages will be based on the number of subjects with a postbaseline evaluation of the specific laboratory test.

Graded lab abnormalities will be also be summarized for the off-treatment period. Lab abnormalities are included starting from 29 days after the last dose of ABI-H2158/PBO.

A by-subject listing of graded laboratory abnormalities will be provided by subject ID number and visit in chronological order. This listing will include all test results that were collected throughout the study for the lab test of interest, with all applicable severity grades displayed.

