1.2. Study Design

This study will assess the safety, antiviral activity, and pharmacokinetics (PK) of ABI-H2158 administered once daily (QD) in combination with ETV in subjects with cHBV. Multiple parallel cohorts will be enrolled in the study.

In Cohort 1, approximately 40 treatment-naïve subjects with HBeAg positive cHBV will be randomized in a 3:1 ratio to receive 300 mg ABI-H2158+ETV (n=30) or matching PBO+ETV (n=10) for 72 weeks (Figure 1-1). In Cohort 2, approximately 40 treatment-naïve subjects with HBeAg negative cHBV will be randomized in a 3:1 ratio to receive 300 mg ABI-H2158+ETV (n=30) or matching PBO+ETV (n=10) for 72 weeks (Figure 1-1). Treatment assignments for Cohort 1 will be stratified by the HBV DNA level measured at the Screening visit (ie, $\geq 8.0 \log_{10}$ IU/mL versus $< 8.0 \log_{10}$ IU/mL) and for Cohort 2 will be stratified by the HBV DNA level measured at the Screening visit (ie, $\geq 6.0 \log_{10}$ IU/mL versus $< 6.0 \log_{10}$ IU/mL).

After completing treatment at Week 72, or following premature treatment discontinuation, all subjects will enter a 24 week follow-up period. During the follow-up period all subjects will remain on ETV and undergo the follow-up assessments. After completing the 24-week follow-up period, all subjects will resume management by their treating physician in accordance with local standard of care.

[figure not shown]
The schedule of assessments is presented in Protocol Appendix 1.

An assessment of PK data will also be performed after all subjects have completed study Week 4 (or discontinued study without completing Week 4) in order to confirm the absence of important drug interactions between ABI-H2158 and ETV at steady state.

Following the early termination of Study ABI-H2158-201, in accordance with the ABI-H2158-201 Protocol Clarification Letter for Amendment 2 dated 14 Dec 2020, 07 September 2021, subjects were instructed to complete the follow-up assessments through 12 weeks after the last dose of study medication.

Throughout the 12-week follow-up period, all subjects should continue treatment with ETV.

Figure 1-1. Study Overview

Abbreviations: PBO: placebo; ETV: entecavir; HBeAg: hepatitis B “e” antigen.

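### SAP 7.2.1.2 gives the off-treatment laboratory table (values from Day 29) a denominator of subjects with values up to Day 28, so its percentages are understated whenever subjects have no later sample

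*Combined protocol and SAP*

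**What the plan says.** SAP 7.2.1.2 begins with the table of treatment-emergent graded abnormalities and then states: "For all summaries of laboratory abnormalities, the denominator is the number of subjects with nonmissing postbaseline values up to 28 days after last dose date" (the dose being ABI-H2158 or placebo). The next paragraph tabulates the worst grade up to 28 days after the last dose and adds that "percentages will be based on the number of subjects with a postbaseline evaluation of the specific laboratory test". Only after that does the section introduce a further table: "Graded lab abnormalities will be also be summarized for the off-treatment period". Its time frame is given as "Lab abnormalities are included starting from 29 days after the last dose of ABI-H2158/PBO". No denominator is attached to it. SAP 3 asks for a number and a percentage for every categorical variable, so a percentage is to be expected.

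On what counts as an event, SAP 7.2.1.1 defines treatment-emergent abnormalities as "values that increase at least 1 toxicity grade from Baseline at any postbaseline time point", within a time frame that ends 28 days after the last dose. Nothing equivalent is written for Day 29 onwards. SAP 7.2.1 grades each value on its own, without reference to Baseline.

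The general definition of off-treatment in SAP 3.6.2 differs from the Day 29 start: the "period is defined after the last dose of ABI-H2158/PBO through the follow up period". After the early termination, SAP 1.2 records that "subjects were instructed to complete the follow-up assessments through 12 weeks after the last dose of study medication".

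**The concern.** The numerator and the denominator of the off-treatment table come from two periods that do not overlap. Someone whose last sample was taken by Day 28 is counted as being at risk in a period when nobody looked. The table then mixes subjects known to be normal with subjects not observed, and reports both as free of abnormality.

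This matters more here than in most Phase 2a plans. SAP 1 says that development stopped after ALT elevations consistent with drug-induced liver injury. Protocol 9.4 asks that all subjects be followed closely for ALT elevations after study drug stops. The confirmed ALT elevation in SAP 7.2.2.1 is defined on treatment. The off-treatment laboratory table is therefore one of the main summaries of liver tests after withdrawal, and an understated percentage there errs towards reassurance. If one arm loses more subjects before Day 29 than the other, the comparison between arms shifts as well.

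**Working it through.** The plan states no off-treatment rate and no expected loss, so there is no figure to reproduce. The check compares the text of the sections and then works out simple proportions.

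**Inputs from the documents**
- Planned size per cohort: 30 on ABI-H2158 and 10 on placebo (SAP 1.3). These set the scale of the illustration only.
- Follow-up visits: 4, 8, 12 and 24 weeks after the last dose, each within 5 days (Protocol 7.5), shortened to 12 weeks after termination (SAP 1.2).

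**Where the visits fall.** Week 4: 28 − 5 = Day 23 to 28 + 5 = Day 33. Week 8: 56 − 5 = Day 51 to 56 + 5 = Day 61. Week 12: 84 − 5 = Day 79 to 84 + 5 = Day 89. The Week 4 visit can lie on either side of the Day 28/29 cut. A subject whose last sample is a compliant Week 4 visit on Days 23 to 28 has no value from Day 29.

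**Formula.** Let N28 be the subjects with a postbaseline value up to Day 28, N29 those with a value from Day 29, and x those with a graded value from Day 29.
- Rate as written: x / N28
- Rate among subjects observed: x / N29
- Ratio, when the N29 subjects are a subset of the N28 subjects: (x / N28) / (x / N29) = N29 / N28

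**Illustration.** N28 = 30 and x = 3. The share without a later sample is assumed.

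| No value from Day 29 | N29 | As written (3/30) | Among observed (3/N29) | Factor |
|---|---|---|---|---|
| 0% | 30 | 10.0% | 10.0% | 1.00 |
| 10% | 27 | 10.0% | 11.1% | 0.90 |
| 20% | 24 | 10.0% | 12.5% | 0.80 |
| 40% | 18 | 10.0% | 16.7% | 0.60 |

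For placebo with N28 = 10 and x = 1, the written rate is 10.0%, against 1/9 = 11.1%, 1/8 = 12.5% and 1/6 = 16.7% at the same losses of 10%, 20% and 40%.

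**Unequal loss (assumed).** Suppose the rate among observed subjects is 20% in both arms, with 20% of ABI-H2158 subjects and no placebo subjects lacking a later sample. The table would show 20% × 0.80 = 16% against 20% × 1.00 = 20%. If the losses are swapped, so is the difference.

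**What the table measures (assumed counts).** If 6 of 24 observed subjects have a graded value from Day 29, the prevalence is 6/24 = 25.0%. If 3 of the 6 already had the abnormality earlier, new or worsened abnormalities are 3/24 = 12.5%. Both are valid answers to different questions, so the table needs a label.

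**The case against.** The best reply is that the Day 28 sentence was never meant for this table. It follows directly on the treatment-emergent summary and comes before the off-treatment table is mentioned. The likelier fault is a forgotten denominator rather than a decision to use the wrong one. That is a fair account of how the text arose, but the sentence says all summaries, and a programmer has nothing else to follow. Nor does borrowing the test-specific denominator from the next paragraph help. It is tied to the Day 28 tabulation, and it too would include subjects never sampled after Day 28.

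A second reply concerns size. Completers and early discontinuers alike enter follow-up, and the Week 8 and Week 12 windows lie wholly after Day 29, so one attended visit with a result is enough. This stands: with full follow-up the error is zero. But SAP 2.2 allows for subjects who discontinue before the 12-week visit, so full follow-up is not assured.

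A third reply is that safety results are descriptive and that other outputs cover the same ground. SAP 7.2.1.2 also requires a chronological by-subject listing of all results with grades. SAP 7.2.2.2 has its own hepatic summary, whose denominator has no Day 28 cut. SAP 7.1.6 tabulates off-treatment adverse events. This limits the consequence but does not correct a printed percentage.

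A reader might go further and infer that the numerator is wrong because abnormalities carried over from Baseline or from treatment are counted. The documents do not support that. The SAP sets no onset or worsening rule from Day 29 and never presents the table as new onset, and counting any graded value is a legitimate prevalence summary. Nor can it be said that a new post-treatment flare is inseparable from a resolving injury, because the listing shows each subject's course.

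**Conclusion.** The denominator point holds on the text as written. The off-treatment percentage equals the rate among subjects observed from Day 29 multiplied by N29/N28: no effect with complete follow-up, 0.90 times at an assumed 10% without later samples and 0.80 times at 20%. The exact factor assumes that everyone sampled from Day 29 was also sampled by Day 28. The amount of loss, and any difference between arms, is not in the documents.

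The point goes no further than that. The numerator is unlabelled, not wrong. No hypothesis test is affected, and individual cases remain visible in the listings. It is an inexpensive correction to make before the SAP is finalised, because the table bears on the safety question that ended development.

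**What to change.** In SAP 7.2.1.2, limit the existing denominator sentence to the treatment-emergent summaries and the worst-grade tabulation up to 28 days. Then add: *For the off-treatment summary, the denominator for each laboratory test is the number of subjects with at least one nonmissing result for that test 29 or more days after their last ABI-H2158/PBO dose.*

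Title the table as the prevalence of any graded value from Day 29, since no worsening rule applies there. Naming the day also avoids confusion with the SAP 3.6.2 definition, under which off-treatment starts right after the last dose.

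A rule counting only grades above both Baseline and the last value up to Day 28 should not be added. A subject with Grade 2 ALT at Baseline, Grade 0 on treatment and a rebound to Grade 2 afterwards would not be counted, although that is a post-treatment flare. Such a Baseline is possible: only ALT above 5 times ULN is excluded (Protocol 5.3), and Grade 2 runs from 2.5 to below 5 times ULN (Protocol Appendix 2).

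The cost is a sentence and a title, with no new data. The downside is slightly smaller denominators in the off-treatment table.
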